Research Code

Radiographic and Clinical Evaluation of Three-Dimensional Delta Plate in Internal Fixation of Mandibular Sub-condylar Fractures.

(Longitudinal Study)

Research Protocol

Submitted to the Department of Oral and Maxillofacial Surgery

Faculty of Dentistry, Ain Shams University.

**In partial fulfillment of the requirements of Masters' degree in Oral
and Maxillofacial Surgery.**

By:

[name]

**B.D.S. Faculty of Dentistry Ain Shams University
2019**

Email: [contact]

Under the Supervision of:

[name].[name]

Professor of Oral and Maxillofacial Surgery
Faculty of Dentistry
Ain Shams University

[name] [name]

Lecturer of Oral and Maxillofacial Surgery
Faculty of Dentistry
Ain Shams University

[name] [name]

Fellow of Oral and Maxillofacial Surgery
Ahmed Maher Teaching Hospital

Year of protocol registration

2023

Table of Contents

Topic	Page
I. Abstract	4
II. Background	5
III. Research Question	8
IV. Aims (Objectives)	9
V. Hypothesis	10
VI. Ethical Considerations	11
VII. Study design	13
VIII. Materials and Methods	14
• Study setting	15
• Sample Size	16
• Study Procedures	17
IX. Statistical Analysis	18
X. Funding of the Study	19
XI. References	20
XII. Arabic summary	23

I. Abstract:

Management of Sub-condylar fractures has been debatable for years, some surgeons advocate closed management if the situation permits, to avoid the complications associated with open reduction and internal fixation (ORIF). Nowadays, there are meticulous approaches and novel osteosynthesis systems that facilitate its open management but many of these systems need more research work to evaluate its efficacy.

In this study we intend to examine the efficacy of 3D delta plates from the radiographic and clinical point of view. This Single arm study will include 14 cases of trauma having mandibular sub condylar fractures, in which open reduction and internal fixation are indicated. After selecting patients according to the inclusion criteria, all patients will undergo open reduction and rigid fixation. Fracture will be stabilized using 4 hole, 2.0 mm 3-D Delta titanium plates using pre-auricular or retromandibular incision.

Postoperative clinical examination will be carried out on day three, day seven, one month and after three months. Postoperative radiographic examination will be performed immediately postoperative by CT scan.

II. Background:

The incidence of mandibular condylar fractures is estimated to be 17.5–52% making it the most seen mandibular fracture (1–4) sub condylar fractures are commonly encountered when the fracture is unilateral. However, in case of bilateral fracture pattern, the condylar heads are the ones that are fractured (5).

The reason for the high incidence of mandibular condyle fracture is attributable to the binding of the mandibular ramus with high stiffness and mandibular condyle head with low stiffness ((6) causative factors include physical trauma, road traffic accidents, violence, fall, sports, and gunshot wound. Internal causative factors include osteomyelitis, benign or malignant tumor, and muscular spasm during electric shock treatment (7).

The management of condylar fractures is highly controversial and includes observation, closed treatment, and open reduction. It depends on multiple factors such as the age of the patient, the co-existence of other mandibular or facial fractures, is it unilateral or bilateral, the level and displacement of the fracture, the stage of dentition and dental occlusion, the facilities in the area, patient's mental and physical conditions ((8).

Closed management of condylar fractures has lots of long-term complications like pain which is considered the most common complaint. In addition to esthetic problems like facial asymmetry due to shortening of ramus especially with unilateral fractures (9). Moreover, Temporomandibular diseases such as ankylosis, internal derangement of the temporomandibular joint (TMJ) and mouth deviation could happen. Nevertheless, Closed management is essential in some cases like simple patterns of fractures when occlusion is achievable, putting into consideration that patient's compliance, mental and physical status are crucial for successful treatment (8). Its main benefit (when indicated) is the avoidance of facial nerve injury, However, facial nerve injury risk is decreased as the operator's experience and skill increase(10) .

Indications for ORIF include bilateral fractures(relative), severe dislocation (> 10 degrees), other facial fractures affecting the occlusion, foreign bodies, lateral displacement of the condyle, and condyle displacement into the middle cranial fossa(11), mandibular nerve paraesthesia(12). Condylar fractures can be reached through trans -facial or intraoral approaches (13,14) .Singh et al (15) published the largest blinded, randomized controlled trial comparing open techniques with closed management; they concluded that both treatment options carry promising outcomes. However, the surgically treated group showed better results in all objective and subjective functional outcomes except for occlusion.

The gold standard osteosynthesis system is the use of two miniplates fixation secured with four screws each (16). However, some drawbacks such as; difficult accessibility that elongates operation time especially in higher fractures the use of double miniplates is associated with risk of facial nerve injury and subsequent facial nerve palsy. Moreover, the little amount of bone that is always encountered at the proximal part of the fracture (17).

Recently, Osteosynthesis devices with various shapes and sizes as single L, Y plate, or 3-D plate are used for the management of condylar fractures. Manufacturers tend to develop such systems to gain outcomes similar to that of the conventional 2 mini-plate system regarding functional stability and rigidity with less cost, less complications and less effort(17).

Several studies were conducted on three-dimensional plating systems such as Rhomboid, Trapezoid and Delta shaped plates that yielded good outcomes (17–21). One study claimed that trapezoidal condylar plate is convenient for low sub condylar fractures because of its wide dimensions, On the other hand, delta plate is suitable for both high and low sub condylar fracture. ((22–24)

The aim of this study is to evaluate the versatility of three-dimensional delta plate in reduction and fixation of this type of fracture in adult patients presented with unilateral sub-condylar fractures for primary ORIF. The results will be analyzed by radiographic assessment of proper anatomical reduction and measurement of vertical ramus height. In addition to, clinical outcomes of pain with jaw movements and measurement of all mandibular movements range.

III. Research Question:

What are the radiographic and clinical outcomes of using three-dimensional Delta plate for primary open reduction and internal fixation of unilateral subcondylar fractures in adult patients?

PICOTS Elements:	
Patient/Problem	Adult patients presenting with unilateral sub condylar fracture, with or without concomitant facial or mandibular fractures.
Intervention	Primary ORIF using three-dimensional delta plate
Comparator	-
Outcome	Pain, posterior facial height, anatomic reduction, mouth deviation.
Time	3 months follow up
Setting	Faculty of Dentistry-Ain Shams University

IV. Aim of the Study, Research Objectives and Clinical Relevance Aim:

The aim of the study is to assess the efficacy of the delta plate in fixation of sub condylar fractures by radiographic evaluation of anatomic reduction and vertical ramus height and clinical evaluation of pain with jaw movements and range of mandibular movements.

Outcomes:

Primary outcomes: 1-Anatomic Reduction
2-Posterior Facial Height

Secondary outcomes: 1-Pain
2-Mandibular Movements.

Clinical Relevance:

Delta plate provides functionally stable osteosynthesis. In addition to, less periosteal dissection, and easier reduction and fixation of small fragments combined with the advantages of a smaller plate size, less cost and adequate stiffness (19,23).

V. Hypothesis:

Delta plate doesn't provide an added advantage over the other Osteosynthesis methods of Sub condylar fixation.

VI. Ethical consideration

Open reduction and internal fixation of sub condylar fractures is accompanied with complications such as facial nerve injury, parotid gland fistula, permanent scar, infection, pain, edema, and difficulty in mastication following surgical procedure.

Risk of Facial injury can be decreased by choosing the appropriate incision and meticulous dissection of the tissues.

Parotid gland fistula is avoided by suturing of parotid capsule or by retroparotid-retromandibular approach whenever possible.

Permanent scar is best minimized by minimal tissue trauma, suturing in layers then the skin will be sutured by Prolene 6-0, Topical antibiotics and topical silicone gel will be prescribed.

Risk of Infection is reduced by post-operative antibiotic.

Post-operative analgesics and anti-inflammatory medications will be given to control pain and edema.

Mastication force is enhanced by physiotherapy.

Patients are allowed to withdraw from the trial whenever they want to. In this case, they will be surgically managed by conventional plating systems. All patients will be fully informed about the procedures. The risks and benefits will be thoroughly explained to them. No surgery will be performed without written consent.

All personal information and data of the patients will be preserved, maintained and stored in a special filing system available in the department. It will not be exposed to anyone that is not included in the surgical team.

The research ethics committee, Faculty of Dentistry Ain Shams University, will review the research plan.

VII. Study Design:

Longitudinal study.

VIII. Materials and Methods:

14 patients having unilateral sub condylar fractures will undergo open reduction and internal fixation by a single 4-hole miniplate 3D Delta plate. The dimensions of this plate are 1.0 mm thick, 20mm long, 5mm wide at top and 14 mm wide at the base. At the top of the plate is an arm with two longitudinally arranged holes, two more holes form the 2 corners of the base of the plate.

Study Setting:

Department of oral and maxillofacial surgery in the Faculty of Dentistry, Ain Shams University.

Sample Size Calculation:

The sample size was estimated based on research published by Manoj et al. study (2015) regarding fracture fixation by trapezoidal 3D plate in India, by fixing alpha at 0.05 (5%) and beta at 0.05(5%), the minimal sample size is 10 patients to be included. To avoid drop out the sample was increased to 14 patients(25).

Eligibility criteria

Inclusion Criteria:

- 1-Patients at or over 18 years.
- 2-Unilateral sub condylar fractures.

Exclusion Criteria:

- 1- Bilateral sub condylar fractures
- 2-Pediatric patients.
- 3-Intracapsular fractures
- 4-Patients with Uncontrolled systematic conditions.

Justification for Exclusions:

- Most clinical and radiographic assessments of bilateral sub condylar fractures are dissimilar to that of unilateral ones.
- The management of pediatric patients is totally different from that of adults.
- Intracapsular fractures is best treated by endoscopic approach or conservatively managed
- Patients with Uncontrolled systematic conditions are unfit for surgery.

Pre-operative Assessment:

All patients will undergo radiographic assessment with Computed Tomography to assess the level of the fracture, degree and direction of displacement and shortening of ramus height by comparing the two sides.

All patients will undergo clinical evaluation of pain, mandible deviation on opening and closing, measurement of mandibular movements.

All patients will undergo pre-operative anesthetic evaluation which includes medical and surgical history, physical examination, investigations, risk assessment, consent and pre-medication.

Surgical Procedure:

All patients will undergo open reduction and internal fixation under general anesthesia.

The Fracture will be exposed either extraorally (submandibular or retromandibular or endaural approaches). The incision will be chosen according to the level of the fracture.

Fracture will be reduced; occlusion will be re checked then it will be fixated by 2.0 mm 3D Delta mini plates and anchored by 4 screws of 7-9 mm length.

Immediate post-operative medications:

All patients will take painkillers, anti-inflammatory, antibiotics and steroids.

Follow up:

Radiographic outcomes: The following will be measured on CT:

1-The vertical ramus height will be done by comparing the two sides from the glenoid fossa to the inferior border of the ramus on CT.

2- Accuracy of anatomical reduction detected on coronal and axial sections.

Radiograph will be taken immediately post-operative.

Clinical outcomes:

1- Assessment of pain by Visual Analogue scale.

2- Mandibular movements by a ruler:

-Lateral mandibular movement by measuring the horizontal distance between upper central teeth midline to the lower central teeth midline.

-Protrusive mandibular movement by measuring the transvere distance between upper central teeth midline to the lower central teeth midline.

-Maximal mouth opening by measuring the vertical distance between upper central teeth midline to the lower central teeth midline.

Follow up notes will be taken on day three, day seven, one month and Three months postoperatively.

IX. Statistical Analysis:

Regarding the continuous date, the T dependent test will be used to assess the statistical data. Regarding the discrete data, Chi Square test will be used to assess the statistical data significance, using SPSS Software.

X. Funding of the Study:

The research study will be self-funded by the operator. No internal or external funding will be shared in this study.

XI. References:

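### The only stated hypothesis compares the delta plate with other fixation methods, but the study has one arm, no comparator and no benchmark, so no planned analysis can test it

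*Protocol*

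**What the plan says.** Section V (Hypothesis) contains one sentence: "Delta plate doesn't provide an added advantage over the other Osteosynthesis methods of Sub condylar fixation". No other hypothesis appears in the protocol.

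The other sections describe a study without a comparison between methods:

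- **Abstract:** "This Single arm study will include 14 cases of trauma having mandibular sub condylar fractures".
- **Section III, research question:** "What are the radiographic and clinical outcomes of using three-dimensional Delta plate for primary open reduction and internal fixation". The comparator row of the PICOTS table below it holds only a dash.
- **Section IV:** the aim is to assess the delta plate. The two primary outcomes are anatomic reduction and posterior facial height; the two secondary outcomes are pain and mandibular movements. No other plate is named as a reference for any of them.
- **Section VIII, opening paragraph:** "14 patients having unilateral sub condylar fractures will undergo open reduction and internal fixation by a single 4-hole miniplate 3D Delta plate".
- **Section VIII, Sample Size Calculation:** the number rests on a published study "regarding fracture fixation by trapezoidal 3D plate in India", and no outcome value from that study is quoted.
- **Section VIII, Pre-operative Assessment:** CT is used to assess, among other things, "shortening of ramus height by comparing the two sides". The post-operative CT repeats the side-to-side comparison.
- **Section IX:** for continuous data, "the T dependent test will be used to assess the statistical data". For discrete data a chi-square test is named, without groups or a reference proportion.

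**The concern.** A hypothesis about added advantage over other methods needs either patients treated by another method or a value fixed in advance that stands for such a method. The protocol provides neither.

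The direction of the wording adds to the problem. Section V is phrased as a null of no added advantage, so a non-significant test in a small series could be reported as supporting it, although that test would contain no information about any other plate. The opposite error is also open: a significant change from before to after surgery could be reported as an advantage of the delta plate, when it shows only that the patients changed.

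For pain and mandibular movements, change up to three months includes natural recovery. That does not apply to the two primary outcomes, which are read on the immediate post-operative CT. Those still reflect the surgical reduction as well as the plate, because section VIII has the fracture reduced before it is fixed.

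**Working it through.** **1. Can any named test address section V?**

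| Route | What it would need | What the protocol gives |
|---|---|---|
| Concurrent comparison | Patients treated with another plate | 0 planned; all 14 receive the delta plate |
| External benchmark | A value or margin for another plate | None, for 0 of 4 outcomes |
| Dependent t-test | Pairs that contrast two methods | Pairs can only be sides, visits, or before and after in the same patient |
| Chi-square test | A second group or a reference proportion | Neither |

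Section VI says that patients who withdraw will be managed with conventional plates. They are not a study group, and no analysis of them is planned. Every route fails.

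**2. Does the stated sample size imply a comparison?**

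The protocol's own figure is "by fixing alpha at 0.05 (5%) and beta at 0.05(5%), the minimal sample size is 10 patients to be included". It cannot be reproduced, because no effect size, SD, rate, margin or sidedness is given. It can only be solved backwards.

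- Paired or one-sample test, n = 10, power 95%, two-sided alpha 0.05, normal approximation: (1.960 + 1.645)/√10 = 3.605/3.162 = 1.14 SD. With the noncentral t distribution: 1.29 SD.
- One-sided: (1.645 + 1.645)/√10 = 1.04 SD. With the noncentral t distribution: 1.13 SD.
- The increase from 10 to 14 corresponds to a loss of up to 1 − 10/14 = 28.6%.

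None of these readings brings in another fixation method. The missing inputs are a separate weakness.

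**3. What would a real comparison need?**

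This is an illustration, since the protocol gives no difference to detect. With two arms, two-sided alpha 0.05 and 95% power, the number per arm is n = 2(1.960 + 1.645)²/d² = 25.99/d².

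| Assumed difference d (SD) | Patients per arm |
|---|---|
| 0.5 | 104 |
| 0.8 | 41 |
| 1.0 | 26 |
| 1.5 | 12 |

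**4. What can the single arm estimate?**

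The 95% half-width for a mean within-patient change, in units of the SD of the change, is t(0.975, n−1)/√n.

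- n = 14: 2.160/3.742 = 0.58 SD.
- n = 10: 2.262/3.162 = 0.72 SD.

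Suppose anatomic reduction is scored yes or no. This is an assumption, because the protocol gives no scale. The exact (Clopper-Pearson) 95% limits are then:

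- 14 of 14: lower limit 0.025^(1/14) = 76.8%.
- 10 of 10: lower limit 0.025^(1/10) = 69.2%.
- 12 of 14: 57.2% to 98.2%.

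These figures show the precision available for a descriptive aim. The contradiction in section V does not depend on them.

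**The case against.** Several points can be made for the protocol.

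- **A single-arm study is legitimate, and only one sentence is out of line.** The title, research question, aim and outcomes are consistently non-comparative, and section IX ties no test to section V. This is true, and it is why the repair is small. But that sentence is the only hypothesis, so it governs how any p-value will be read.
- **A benchmark could be set in a statistical analysis plan that is not shown.** A plan could hold a reference value. It could not create a comparator arm, and a benchmark placed there would still contradict the dash in the comparator row and the descriptive research question.
- **The background names two miniplates as the standard method, and the reference list includes clinical comparisons of delta plates with other plates.** No result from these sources is carried into the protocol as a reference value.
- **The chi-square test can be run in one sample against a fixed proportion.** It can, but no proportion is stated.
- **A null of no change in ramus-height difference after open reduction is a weak replacement.** This stands. Rejecting it says little, so the residual post-operative difference with its confidence interval should carry the result.
- **A new objective leaves the sample-size statement without its purpose.** This also stands, and the fix includes it.

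**Conclusion.** The concern holds. Section V states a between-method hypothesis that the protocol's own design and analysis cannot test: no patients on another plate are planned for analysis, and none of the four outcomes has a value or margin for another plate. Neither a significant nor a non-significant result would bear on it. The conclusion follows from the protocol's text and needs no numerical assumption. Only the proportions shown for anatomic reduction depend on an assumed yes/no scale. Because the defect affects the main conclusion that the study could report, it should be corrected even though the correction is short.

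**What to change.** 1. **Replace section V** with an objective that matches the research question. One option is a within-patient null: the side-to-side difference in ramus height does not change between the pre-operative and the immediate post-operative CT. Lead the report with the residual post-operative side-to-side difference and its 95% confidence interval.
2. **Report the other outcomes as estimates.** Anatomic reduction, and pain and mandibular movements to three months, should be given with 95% confidence intervals.
3. **State the limits of inference.** No conclusion of advantage, equivalence or lack of advantage against other plates will be drawn, and any comparison with published series is descriptive. Change in pain and movement includes natural recovery, and the immediate CT reflects the surgical reduction as well as the plate, so neither is attributed to the plate alone.
4. **Re-tie the sample-size paragraph** to the new objective, or replace it with a precision statement such as ±0.58 SD with 14 patients and ±0.72 SD with 10.

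This costs protocol wording only. Both CTs are already planned, and patients, visits, imaging and the number enrolled do not change. The price is a more modest claim. If a comparative claim is wanted, the alternative is a concurrent comparator, or an external value fixed in advance, with a new sample-size calculation. That would be a different and probably larger study.

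### The 95% power claimed for 10 patients is tied to no outcome, contrast or effect, and cannot apply to the protocol's only hypothesis, which is comparative in a single-arm study

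*Protocol*

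**What the plan says.** Protocol section VIII, Sample Size Calculation, rests the size on one published study "regarding fracture fixation by trapezoidal 3D plate in India" and states that "by fixing alpha at 0.05 (5%) and beta at 0.05(5%), the minimal sample size is 10 patients to be included". The number is then raised to 14 to allow for drop-out. No figure from the cited study is given.

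The parts of the protocol that this calculation could refer to are:

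- **Design.** Section I: "This Single arm study will include 14 cases of trauma having mandibular sub condylar fractures". The comparator entry in the PICOTS table (section III) is a dash.
- **Aim and outcomes.** Section IV: "The aim of the study is to assess the efficacy of the delta plate in fixation of sub condylar fractures by radiographic evaluation". The list that begins "Primary outcomes: 1-Anatomic Reduction" has posterior facial height as its second item.
- **Hypothesis.** Section V says that the delta plate does not "provide an added advantage over the other Osteosynthesis methods of Sub condylar fixation".
- **Ramus height before surgery.** Pre-operative Assessment uses CT for "degree and direction of displacement and shortening of ramus height by comparing the two sides".
- **Ramus height after surgery.** Under Follow up, radiographic outcomes, the "vertical ramus height will be done by comparing the two sides from the glenoid fossa to the inferior border of the ramus", on a CT taken immediately after the operation.
- **Tests.** Section IX assigns a dependent t-test to continuous data and a chi-square test to discrete data. It does not say what is compared with what.

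**The concern.** A 5% beta is a promise about a particular test of a particular effect. Here neither is named, so a reader cannot tell what the 95% assurance covers. Three readings are possible, and each allows a different conclusion:

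1. Delta plate against other methods, as the hypothesis is worded.
2. Injured against uninjured side after surgery, which is how ramus height is measured.
3. Shortening or displacement before against after surgery, since both are assessed on the pre-operative CT.

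The stated aim is to assess efficacy. If the 95% figure is carried into the report without a contrast, it can lend confidence to conclusions that the study cannot reach, such as parity with other plates or restored ramus height.

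**Working it through.** **Inputs from the protocol.** Alpha 0.05, beta 0.05 (power 0.95), minimum N=10, planned N=14, dependent t-test for continuous data, one arm. Not given: outcome, contrast, effect, SD, sidedness, margin, reference value.

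**Step 1. Can N=10 be reproduced?** Not forwards, because no effect or SD is given. It can be solved backwards for a dependent t-test with normal differences. Let δ be the mean paired difference divided by the SD of the differences. Two-sided power is P(|T| > t₀.₉₇₅,ₙ₋₁), where T is noncentral t with n−1 df and noncentrality δ√n. One-sided power uses t₀.₉₅,ₙ₋₁ and the upper tail only.

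| δ needed for 95% power | n=9 | n=10 | n=14 |
|---|---|---|---|
| Two-sided 5% | 1.379 | 1.286 | 1.044 |
| One-sided 5% | 1.206 | 1.131 | 0.930 |

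Ten is the smallest adequate number when δ is large enough for n=10 but too small for n=9. That means 1.29-1.38 two-sided, or 1.13-1.21 one-sided. For smaller assumed effects the minimum (two-sided/one-sided) would be 16/13 at δ=1.0, 26/21 at δ=0.75 and 54/45 at δ=0.5. N=10 is therefore consistent with a large paired change, but nothing in the protocol says that such a change was assumed.

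**Step 2. The comparative hypothesis.** A test of it needs data on another fixation method, or a fixed reference value. The protocol has one arm, a dash as comparator and no reference value. No within-patient test bears on this hypothesis at any N, so no power figure from this study can attach to it.

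**Step 3. If the post-operative side difference is the tested contrast.** Success is a difference near zero, whereas power is the chance of declaring a difference. By Step 1, a 5% beta at n=10 speaks only to a residual difference of about 1.29 SD or more (two-sided). The chance of a non-significant two-sided result, 1 − power, for assumed residual shortening is:

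| Residual shortening (assumed) | n=10 | n=14 |
|---|---|---|
| 0.25 SD | 1 − 0.109 = 89% | 1 − 0.140 = 86% |
| 0.5 SD | 1 − 0.293 = 71% | 1 − 0.410 = 59% |
| 0.75 SD | 1 − 0.562 = 44% | 1 − 0.737 = 26% |
| 1.0 SD | 1 − 0.803 = 20% | 1 − 0.932 = 7% |

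The 95% CI half-width for a mean paired difference, in SD units, is t₀.₉₇₅,ₙ₋₁/√n:

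- n=10: 2.262/3.162 = 0.72 SD
- n=14: 2.160/3.742 = 0.58 SD

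**Step 4. If the pre/post change is the tested contrast.** Power to detect a difference is then the right kind of assurance, and Step 1 shows what change N=10 requires. A significant change shows that shortening fell. It does not show that none remains.

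**Step 5. If anatomic reduction is scored as discrete.** Steps 1, 3 and 4 do not apply to it. The precision would be that of a proportion. For example, if every patient succeeded, the exact 95% lower limit would be 0.025^(1/n), which is 0.69 at n=10 and 0.77 at n=14.

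**The case against.** Several points on the other side carry weight.

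- **N=10 may be right.** The cited study may contain the inputs. A reader might infer from the missing details that ten is too few. The protocol does not support that, because a change of about 1.3 SD would justify it.
- **The t-test is not assigned to the side difference.** A reader might infer that the plan tests the two sides after surgery and would take a non-significant result as restored height. Neither step is written. Comparing sides may simply be how shortening is measured, before surgery as well as after, and a pre/post test is an equally natural contrast in a study labelled longitudinal. This stands, so Step 3 is conditional.
- **The power is not expressly attached to the hypothesis.** This is true, and the research question in section III is descriptive. But section V is the only hypothesis in the protocol, and the calculation names no other target. The mismatch between hypothesis and design remains either way.
- **The residual-shortening rates are assumptions.** The protocol gives no SD or margin, and at 1.0 SD the rates fall to 20% and 7%. The n=10 column may also be pessimistic for the radiographic outcomes, because the CT is taken immediately after surgery and loss to follow-up over three months should hardly affect it.
- **Such details could sit in a separate analysis plan.** Missing detail alone would not be a finding. The protocol, however, makes the power claim itself and uses it to set enrolment, beside a hypothesis that the design cannot test.

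**Conclusion.** The point holds in a limited form. The 95% power at N=10 cannot be reproduced and is linked to neither primary outcome. It cannot apply to the comparative hypothesis, and that part rests on the protocol's own text and needs no assumption.

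For ramus height the conclusion depends on the contrast. For the post-operative side difference, power without a stated margin gives no assurance of restored height. For the pre/post change, power is appropriate once its inputs are given, but a significant result is not evidence of full restoration.

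The stronger statements, that ten patients is the wrong number or that power is the wrong basis for ramus height under every reading, are not supported. The calculations assume normally distributed paired differences, and the effect sizes are illustrative. This should be fixed, because it changes what the study can claim and costs almost nothing.

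**What to change.** 1. **Hypothesis (section V).** Restate it as within-patient or descriptive, and say that the study does not test superiority or equality against other plates.
2. **Sample size (section VIII).** Choose one of two courses. Either withdraw the 95% power statement and give the precision: a 95% CI half-width for a mean paired difference of 0.58 SD with 14 patients and 0.72 SD with 10. Or limit the statement to a named pre/post contrast (ramus shortening or displacement), with its expected change, SD, test and sidedness, so that N=10 can be recomputed. Precision may be added in the second case but is not required.
3. **Ramus height (section IX).** Report the post-operative side difference with its 95% CI, and do not rely on a dependent t-test alone.
4. **Anatomic reduction.** The half-widths above apply to continuous measures only. If this outcome is scored as discrete, report the proportion with an exact 95% CI.

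The cost is protocol wording and one added summary, with no additional patients, visits or scans. The downside is a less favourable stated assurance: with 10 to 14 patients, ramus height may only be describable to within about 0.6-0.7 SD.
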